### 7.4.3 Study Device Administration

Subjects are physically masked (blindfolded) just prior to and during all injection procedures including the application of the LMX4 or inert cream to prevent observation of the syringes containing study device and the topical product. Any unblinded investigators and staff should be reminded NOT to discuss the treatment in the presence of the subject. Subjects will maintain the unique subject number previously assigned in Protocol PRO 2018-02 and PRO 2018-03.

The subject should be positioned in a seated position and may be reclined to as much as 45°.

Any makeup should be removed with a gentle cleanser or a specific makeup remover product (such as Neutrogena Cleansing Makeup Remover Facial Wipes).

The non-vermillion areas of the upper and lower lips should be prepared by gentle washing with a surgical scrub product (Chlorhexidine, Technicare, etc.).

To maintain the subject blinding, the upper and lower lip, upper and lower vermillion and any planned injection areas in or around the mouth corners should be covered with a liberal application of either the Sponsor provided inert cream or the topical anesthetic according to the randomization code. The designated cream product should be applied in a layer thick enough

that no skin or lip color is visible through the product. Investigators should use as much cream as necessary to achieve this result and not be limited to the contents of one tube of product.

Wait 15 minutes before treatment administration.

The anesthetic cream or inert cream should be removed by wiping firmly with a dry gauze before injecting. Only the area to be immediately treated should be wiped clear of cream. Areas not yet treated should remain covered with cream until moments prior to undergoing injection.

To prepare the syringes for use, the investigator should attach one of the needles included in the subject study device kit in a firm manner. The plunger should be gently depressed to express any unwanted air until a small droplet of implant material appears at the tip of the needle.

Study device is administered using only a needle provided in the subject study device kit. The needle is inserted at an approximate angle of 30° parallel to the surface of the skin or lip. For rhytids, study device should be injected into the mid-to-deep dermis. Study device should be injected into the submucosal layer for lip augmentation; care should be taken to avoid intramuscular injection. If study device is injected too superficially this may result in visible lumps and/or bluish discoloration.

Inject study device applying light to moderate, even pressure on the plunger. Avoid injecting quickly as rapid injection can result in increased pain. It is important that the injection is stopped just before the needle is pulled out of the skin to prevent material from leaking out or being too superficially implanted into the skin.

Only correct or augment to 100% of the desired volume effect. Do not overcorrect or overfill.

The needle may be replaced as needed to ensure subject comfort. Only needles provided in the subject study device kit may be used. Before needle replacement, the plunger should be withdrawn slightly and once the needle has been replaced, the plunger re-advanced to ensure that the new needle is prefilled with implant material prior to restarting injections.

Typical usage for each treatment session is specific to the site as well as the amount of augmentation or rhytids correction desired. Based on U.S. clinical studies, the maximum volume allowed per treatment is 1.5 mL per lip (1.5 for upper, 1.5 for lower) and 1.0 mL for perioral rhytid correction. Thus, the maximum amount that can be used at one treatment session is 4.0 ml.

Amounts of material injected should be recorded separately for the upper lip, lower lip, and perioral areas.

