## 7.4.5 Method of Packaging, Labeling, Storage, and Dispensing

For PN40082, one 1.0 mL syringe is packaged along with two fine-gauge needles (30G) in an easy-open tray. Each syringe is equipped with a Luer-Lok as well as a custom finger grip and plunger rod. The syringes contain a peelable label to be placed on the subject record for tracking purposes. Two trays are packaged in a carton. A label that includes the protocol number and Sponsor name will be attached to each carton.

For RV001 with topical anesthetic, one 1.0 mL syringe is packaged along with two fine-gauge needles (27G) in an easy-open tray. 30G fine-gauge needles will be provided in bulk by the Sponsor for use instead of the 27G needles. Each syringe is equipped with a Luer-Lok as well as a custom finger grip and plunger rod. The syringes contain a peelable label to be placed on the subject record for tracking purposes. Two trays are packaged in a carton. A label that includes the protocol number and Sponsor name will be attached to each carton. Bulk commercial supplies of LMX4 will be provided.

For RV001, one 1.0 mL syringe is packaged along with two fine-gauge needles (27G) in an easy-open tray. 30G fine-gauge needles will be provided in bulk by the Sponsor for use instead of the 27G needles. Each syringe is equipped with a Luer-Lok as well as a custom finger grip and plunger rod. The syringes contain a peelable label to be placed on the subject record for tracking purposes. Two trays are packaged in a carton. A label that includes the protocol number and Sponsor name will be attached to each carton. To confirm use of the 30G needles, the 27G needles should remain in the retained packaging for reconciliation.

All study device will be stored in a climate-controlled, limited access area.

The investigator agrees to store and administer the study device only at the site(s) listed on Form FDA 1572 (or investigator agreement/statement). The investigator, sub-investigator(s), or qualified designees also agree that the study device will be administered only to subjects who have provided written informed consent and have met all entry criteria. The study device may not be used for any purpose other than as stated in the protocol.

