#### 5. Warnings

For external use only.

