#### Do not use

- in or near the eyes
- in large quantities, particularly over raw surfaces or blistered areas

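### The open-ended cream instruction in Section 7.4.3 is not reconciled with the large-quantity warning in the appended LMX4 insert, and no provision asks for the cream amount to be recorded

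*Combined protocol and SAP*

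**What the plan says.** Section 7.4.3 has the lips, the vermilion and any planned injection areas at the mouth corners "covered with a liberal application of either the Sponsor provided inert cream or the topical anesthetic according to the randomization code". The end point is visual: the layer must be thick enough "that no skin or lip color is visible through the product". On quantity, the section says: "Investigators should use as much cream as necessary to achieve this result and not be limited to the contents of one tube of product". No weight, volume, number of tubes or maximum is given.

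The LMX4 package insert is part of the same protocol, as Appendix 4. Its Do not use list includes use "in large quantities, particularly over raw surfaces or blistered areas", and the Drug Facts panel reproduced in that appendix repeats the warning. Neither place says what quantity counts as large.

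On supply, Section 7.4.5 says only: "Bulk commercial supplies of LMX4 will be provided". Section 7.4.1 likewise refers to commercial stock and names no tube size.

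On recording, Section 7.4.3 is explicit for the gel: "Amounts of material injected should be recorded separately for the upper lip, lower lip, and perioral areas". The same section caps the gel at 4.0 mL per session. There is no parallel sentence for the cream.

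**The concern.** A site holding this protocol has two texts on the amount of LMX4 and nothing that says how they fit together. One leaves the amount to whatever full coverage takes. The other warns against large quantities. That is an unreconciled passage on the handling of an active drug, in the one arm that receives it.

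The statistical side is exposure. Section 7.9.1 and the Safety Analysis part of the Synopsis plan to compare adverse events between subjects whose injections contained lidocaine and the group given topical lidocaine. For the first group, the lidocaine given can be worked out from the recorded injected volume. For the second, no amount will be available unless someone writes it down on the day. If a local or systemic event occurs in the topical arm, or the adverse-event profiles differ, the report could not say how much cream the subjects had or whether sites used it consistently. This cannot be reconstructed later.

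**Working it through.** The plan states no figure for cream quantity, so there is none to reproduce. The check is a reading of the texts against each other, with a little arithmetic to show what is left open.

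**1. Instruction against warning**

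| Item | Section 7.4.3 | Appendix 4 (LMX4 insert) |
|---|---|---|
| Product covered | Active or inert cream, by randomization | LMX4 only |
| Amount | Whatever coverage requires; one tube is not a limit | Not in large quantities |
| Numerical limit | None | None |
| Reference to the other text | None | Not applicable |

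The two overlap only where the assigned cream is LMX4, that is, in the RV001 with topical anesthetic arm. Randomization is 1:1:1 (Section 7.4.2), so this is about one third of subjects. The Synopsis anticipates fewer than 158 in all, and 158 / 3 = 52.7, so the arm would have at most about 52 subjects.

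**2. What one tube means**

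The insert gives a strength of 40 mg lidocaine per gram and lists tubes of 5, 15 and 30 g. Lidocaine per tube = tube weight × 40 mg/g:

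- 5 g × 40 mg/g = 200 mg
- 15 g × 40 mg/g = 600 mg
- 30 g × 40 mg/g = 1,200 mg

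The range is six-fold (1,200 / 200), and the documents do not say which size is supplied. These figures are tube contents. They are neither the amount placed on the lips nor the amount absorbed.

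**3. What is known about the injected arm**

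The gel cap is 1.5 + 1.5 + 1.0 = 4.0 mL, and PN40082 contains 0.3% w/w lidocaine, or 3 mg/g. Gel density is not given. Assuming 1.0 to 1.05 g/mL, the cap corresponds to 4.0 × 1.0 × 3 = 12.0 mg up to 4.0 × 1.05 × 3 = 12.6 mg. Injected lidocaine is therefore capped, and it can be recovered per subject from the recorded volume.

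**4. Does any recording provision reach the cream?**

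| Provision | What it captures |
|---|---|
| Section 2, Schedule of Activities | That cream is applied 15 minutes before treatment; no quantity |
| Section 7.4.3 | Injected volume by area |
| Section 7.4.7, concomitant medications | Name and indication; no amount |
| Section 7.4.8, compliance | Administration of the study device on the CRF |
| Section 10.2.1, Study Device Dispensing Log | Lot number and amount of study device per subject |

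Whether the last two cover the cream depends on whether it counts as study device. Sections 7.4.3 and 7.6.1 name the topical product separately from the device, so on their wording they do not. No provision asks for grams, tubes or tube size.

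**The case against.** The best counter-argument is that the texts do not contradict each other. The insert never defines large. It also allows application several times a day and under an occlusive dressing, whereas the trial applies the cream once. Section 7.4.3 bounds use in its own way: a named area, a visible end point, a fixed wait, and removal before each site is injected. Treating Investigators are board-certified specialists, and the exclusion criteria cover amide-anesthetic hypersensitivity and concurrent lidocaine regimens. All of this stands. A reader might infer that the protocol orders sites to exceed one tube, or to breach the insert. It does neither: going beyond one tube is allowed, not required, and no amount in the documents can be shown to be too large. What remains is an open-ended instruction beside an unquantified warning, with no sentence linking them.

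Second, the analytic harm is limited. Both creams follow the same coverage rule and wait, allocation is randomized, and results are summarized descriptively. A reader might infer that unrecorded cream amounts bias the pain comparison. They do not: the arms are compared as regimens, and the cream as applied is part of the regimen. The gap affects description and interpretation only.

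Third, setting tube content against the injected dose might suggest a very large excess exposure in the topical arm. That does not follow, because content is not the amount applied, the route differs, and absorption is unknown.

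Fourth, the CRF is not among the documents, and the Synopsis lists RV001 with a topical anesthetic under Study Device, so the log might in practice include the cream. The claim is therefore limited to this: no provision in the protocol calls for the amount.

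**Conclusion.** The point holds as a reconciliation and recording gap. Section 7.4.3 and the Appendix 4 warning need to be brought together, and the amount of cream used is not called for anywhere, although a planned safety comparison rests on topical against injected lidocaine. It concerns one of three arms. The only numerical content is that an unspecified tube may hold 200, 600 or 1,200 mg lidocaine.

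This is a low-cost improvement and not a threat to the trial's validity. The conclusion assumes that the CRF adds no cream-amount field beyond what the protocol asks for, and that study device does not include the topical product, as Sections 7.4.3 and 7.6.1 suggest. If either assumption is wrong, the recording part falls away and the unreconciled text remains.

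**What to change.** 1. The sponsor should reconcile Section 7.4.3 with the Appendix 4 warning so that sites have one consistent text. The content is for the sponsor's medical team; no amount is proposed here.
2. State the LMX4 tube size supplied in Section 7.4.5, so that references to a tube have a fixed meaning.
3. Have the unblinded Treating Investigator record tube size and amount of cream used for every subject, active or inert, in the same format in all arms. Keep the entry away from the blinded Evaluating Investigator.
4. Summarize the amount descriptively by arm beside the TEAE tables. It is measured after randomization, so it should describe exposure and not serve as an adjustment variable in the arm comparisons.

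The cost is a wording change, about one added CRF field and slightly more work at the treatment visit. No change to sample size, randomization or the planned comparisons is needed.

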## INJECTION TECHNIQUES

- 1. Study device can be injected by a number of different techniques that depend on the treating investigator's experience and preference and subject characteristics.
- 2. **Serial puncture** involves multiple, closely spaced injections along wrinkles, folds, or the vermillion border. Although serial puncture allows precise placement of the filler, it produces multiple puncture wounds that may be undesirable to some subjects.
- 3. **Linear threading (includes retrograde and antegrade)** is accomplished by fully inserting the needle into the center of the area to be corrected or augmented and injecting the filler along the track as a "thread." Although threading is most commonly practiced after the needle has been fully inserted and is being withdrawn, it can also be performed while advancing the needle (antegrade technique). To augment the lip, the retrograde

- linear threading technique is the most advisable.
- 4. Serial threading is a technique that utilizes elements of both approaches.

  Note! The correct injection technique is crucial for the final result of the treatment.
- 5. The following techniques should be avoided as they may result in an increase in short-term episodes of bruising, swelling, redness, pain, or tenderness at the injection site:
  - Dissection of the sub-epidermal plane with lateral movement of the needle "fanning"
  - Rapid flow rate (> 0.3 mL/min) of implant material injection
  - High injection volumes
  - The use of needles other than ones provided in the subject study device kit
- 6. The use of cannulas is prohibited.
- 7. Efforts should be made to keep the injection procedure similar between subjects. It is understood that each subject is somewhat different but each investigator should strive to use the same techniques for each subject. Additionally, the number of needle insertions should be kept to the minimum necessary for each subject.
- 8. When the injection is completed, the treated site should be **gently** massaged so that it conforms to the contour of the surrounding tissues. Massaging that substantially deforms the lips or causes blanching of compressed tissues is excessive and should be avoided except as described below.
- 9. If excessive material is implanted or irregularly implanted, massage the area somewhat more firmly than for the usual implantation procedure to obtain optimal results.
- 10. If blanching of the tissues is observed during or directly after injection and becomes a concern, the area may be gently massaged. If blanching persists, contact the Medical Monitor.
- 11. The lips should be augmented to achieve the maximum desirable appearance for both the treating investigator and the subject. Subjects should be provided a small hand mirror to observe the results and further injections conducted until maximum benefit has been obtained. Care should be taken to ensure that the lips are symmetric from right to left and that the upper and lower lips have relative proportionality.
- 12. The perioral area should be corrected AFTER the upper and lower lips have been corrected. Some correction of perioral rhytids may occur with lip augmentation, thus it is best to address any remaining perioral correction needs after the lip injections have been completed.
- 13. If the treated area is swollen directly after the injection, an ice pack can be applied on the site for a short period if the investigator deems it appropriate. Ice should be used with caution if the area is still numb from anesthetic to avoid thermal injury.
- 14. Subjects should be encouraged to avoid a recumbent position for several hours after injections to reduce swelling. The use of ice, cold packs or other therapies to reduce swelling should only be performed at instruction of the investigator. The subject should be instructed to contact the site if substantial swelling occurs.

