#### 7.9.6.3 Reference Safety Information for Assessing Expectedness of Adverse Events

For reference safety information for assessing the expectedness of an AE for the study device in this study, see Appendix 2: PN40082 Instructions for Use and Appendix 3: RV001 Instructions for Use.

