## Preparation:

- The above materials should be gathered and labeled for emergency use only (to ensure they are available should an urgent situation arise).
- Staff should be educated regarding the urgent nature of such an event and the location of all materials and contact information.
- Investigators may wish to familiarize themselves with the retrobulbar injection technique via literature or on line training.

It is critical to recognize any intravascular events during injections and act quickly to maximize likelihood of reversal. As soon as an intravascular is recognized, **stop any further injections**.

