## INJECTION TECHNIQUES

- 1. Study device can be injected by a number of different techniques that depend on the treating investigator's experience and preference, and patient characteristics.
- 2. **Serial puncture** involves multiple, closely spaced injections along wrinkles, folds or the vermillion border. Although serial puncture allows precise placement of the filler, it produces multiple puncture wounds that may be undesirable to some patients.
- 3. **Linear threading (includes retrograde and antegrade)** is accomplished by fully inserting the needle into the center of the area to be corrected or augmented and injecting the filler along the track as a "thread." Although threading is most commonly practiced after the needle has been fully inserted and is being withdrawn, it can also be performed while advancing the needle antegrade technique). To enhance the lip, the retrograde linear threading technique is the most advisable.
- Serial threading is a technique that utilizes elements of both approaches.
   Note! The correct injection technique is crucial for the final result of the treatment.
- 5. The following techniques should be avoided as they may result in an increase in short-term episodes of bruising, swelling, redness, pain, or tenderness at the injection site:
  - Dissection of the sub-epidermal plane with lateral movement of the needle "fanning"
  - Rapid flow rate (>0.3 mL/min) of implant material injection
  - High injection volumes
  - The use of needles other than those provided in the treatment kit
- 6. The use of cannulas is prohibited
- 7. When the injection is completed, the treated site should be **gently** massaged so that it conforms to the contour of the surrounding tissues. Massaging that substantially deforms the lips, or causes blanching of compressed tissues, is excessive, and should be avoided except as described below.
- 8. If excessive material is implanted or irregularly implanted, massage the area somewhat more firmly than for the usual implantation procedure to obtain optimal results.

- 9. If blanching of the tissues is observed during or directly after injection, pause the procedure and massage the area gently until the color returns. If the condition persists, contact the Medical Monitor.

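### For blanching at injection, Section 7.4.3 no. 10 is weaker than the device instructions in Appendices 2 and 3: massage is optional and conditional, with no pause and no end point.

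*Combined protocol and SAP*

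**What the plan says.** Three places in the protocol tell the injector what to do when tissue blanches.

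- Section 7.4.3, Injection Techniques no. 10, applies to every arm. If blanching is seen and "becomes a concern, the area may be gently massaged. If blanching persists, contact the Medical Monitor".
- Appendix 2 (PN40082 instructions for use), Injection Techniques no. 9: on seeing blanching, "pause the procedure and massage the area gently until the color returns. If the condition persists, contact the Medical Monitor".
- Appendix 3 (RV001 instructions for use), Injection Techniques no. 23: the same words as Appendix 2. This covers both RV001 arms.

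A fourth place deals with the next stage. Appendix 1, the filler first aid protocol, says under Preparation: "It is critical to recognize any intravascular events during injections and act quickly to maximize likelihood of reversal". Once such an event is recognized, the order is to "stop any further injections". Section 7.9.3.4 refers to Appendix 1 in its text on embolic, ischemic and visual events.

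The only place where the protocol body cites Appendices 2 and 3 is Section 7.9.6.3, and there the purpose is narrow: "For reference safety information for assessing the expectedness of an AE for the study device in this study".

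**The concern.** One sign has two standards inside one protocol, and the softer one is in the section an injector would naturally work from. Blanching can be harmless, but it can also be an early sign of a blocked vessel. Appendix 1 itself pairs blanching with ischemia in its skin infarction steps. The Warnings in Appendices 2 and 3 list superficial necrosis and scarring as possible results of injecting into or close to a vessel, and name the lips among the sites.

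At stake is the interval between first seeing blanching and deciding whether it is vascular. An injector using Section 7.4.3 alone is not told to interrupt the session in that interval. The device instructions tell the same injector to pause and not to end the massage before color is back. The subjects are having an elective cosmetic procedure, so there is little reason for the body of the protocol to carry the less cautious rule.

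**Working it through.** No arithmetic applies, and the plan states no figure to reproduce. The check is a comparison of the texts, followed by a search for anything elsewhere that closes the gap.

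**Step 1. The instructions side by side.**

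| Element | Section 7.4.3 no. 10 | Appendix 2 no. 9 and Appendix 3 no. 23 |
|---|---|---|
| What triggers massage | Blanching seen, and judged a concern | Blanching seen |
| Pause | Not mentioned | Directed |
| Massage | Permitted | Directed |
| End point of massage | None given | Return of color |
| If blanching persists | Medical Monitor is contacted | Medical Monitor is contacted |

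The concern qualifier belongs to the massage sentence. The escalation sentence in no. 10 stands by itself and carries no such condition. The rows describe where the wording differs. They overlap and are not a measure of risk.

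**Step 2. Is the softer wording part of a general difference between the body and the appendices?** No. Items 8, 9, 11 and 12 of the Section 7.4.3 list reappear essentially unchanged as nos. 7, 8, 10 and 11 in Appendix 2 and nos. 21, 22, 24 and 25 in Appendix 3. Within that run only the blanching item differs in substance, and the documents give no reason for it.

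**Step 3. Does another item in the Section 7.4.3 list supply the pause?** No. Item 8 begins "When the injection is completed, the treated site should be" and asks for gentle massage to shape the contour, so it applies after the injection. Item 11 has "further injections conducted until maximum benefit has been obtained". Both items also appear in the appendices, so they do not make Section 7.4.3 worse than its counterparts. They show only that nothing else in the list does the work of the missing pause.

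**Step 4. Does the protocol say which text governs?** No. Section 7.9.6.3 uses the appendices for judging expectedness. Section 7.6.1 makes the Treating Investigator responsible for administration under the protocol and other study instructions, without naming the appendices or ranking them.

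**Step 5. Does Appendix 1 close the gap?** Partly. Its stop order starts when an intravascular event is recognized, and its skin infarction steps start when an infarction has been identified. Blanching that has not yet been classified falls before both.

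**Step 6. How many subjects?** This cannot be computed. The documents give no frequency of blanching and no probability that blanching turns out to be vascular. The wording applies in all three arms.

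**The case against.** The strongest reply is that the stricter rule is already in the protocol. Appendices 2 and 3 are part of the document and act as study instructions: Appendix 3 says when to apply the topical anesthetic to subjects randomized to it, and which needles the study uses. An injector who follows them also satisfies no. 10. Harm needs an injector who reads Section 7.4.3 and disregards the device instructions, and Section 7.6.1 requires that injector to be a board-certified dermatologist or plastic surgeon. The qualifier also has a plausible reason. Item 8 says that massage that "causes blanching of compressed tissues is excessive and should be avoided", which shows that pressure alone can blanch tissue.

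Much of this stands. The texts are compatible, the injectors are qualified, and a recognized vascular event is already covered. What remains is that the protocol body leaves to judgement what the sponsor's own device instructions direct, without explanation and without saying which prevails. Compression blanching justifies expecting some false alarms. It does not explain leaving out a brief pause.

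A reader might infer that no. 10 does nothing unless blanching is judged a concern. It does not say that, because the escalation sentence is unconditional. A reader might also connect this to Section 7.9.9, where whether the investigator followed a treatment SOP decides if an embolic event suspends one site or the whole study. The documents do not identify that SOP. It may be a separate text that already deals with blanching, so no conclusion about suspension can be drawn.

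**Conclusion.** The point holds in a limited form. For blanching seen during or just after injection, Section 7.4.3 no. 10 is less protective than Appendix 2 no. 9 and Appendix 3 no. 23: massage is optional and conditional, there is no pause, and there is no end point. Escalation is the same. The gap covers only blanching not yet judged vascular, in all three arms, and the number of subjects affected is unknown.

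The conclusion assumes that some injectors will work mainly from Section 7.4.3, which is reasonable because that section sets out study device administration. It does not support reading the protocol as contradictory, or as lacking a stop rule for recognized intravascular events. It has no bearing on the statistical analysis. It is a safety wording inconsistency that should be corrected because the safer rule is already written and the correction is cheap.

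**What to change.** Replace the action in Section 7.4.3 no. 10 with the wording of Appendix 2 no. 9 and Appendix 3 no. 23. The trigger becomes observed blanching without the concern qualifier, and the instruction becomes "pause the procedure and massage the area gently until the color returns. If the condition persists, contact the Medical Monitor". Leave Appendices 1, 2 and 3 as they are.

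Optionally add a cross-reference: once an intravascular event is recognized or a skin infarction identified, follow Appendix 1. Keep those triggers. Sending the injector to Appendix 1 on suspicion alone would set the body against the appendix on when its treatment steps, including nitroglycerin paste and aspirin 325 mg, begin.

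The cost is a wording amendment with IRB approval (Sections 9.2 and 10.5), notice to the five sites, and some short pauses for blanching that proves to be simple compression.
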